5.12.2. Second Key Secondary Efficacy Analysis

5.12.2.1. Estimand

The second key secondary estimand has the following attributes:

1. Treatments as randomized
2. Full analysis set as the primary population of interest
3. The change from baseline in panic attack frequency during the last two weeks of the Maintenance Treatment as the endpoint of interest
4. The population level summary of interest is the estimated treatment differences in median and the 95% confidence interval using Hodges-Lehmann estimation
5. While-on-treatment strategy with data prior to treatment discontinuation used in the analysis

5.12.2.2. Main Analytic Method

The change from Baseline to each analysis period in frequency of panic attacks will be summarized by analysis period and treatment group using descriptive statistics. Estimated treatment differences in median and the 95% confidence interval using Hodges-Lehmann estimation will also be reported. A non-parametric analysis using Mann-Whitney test performed on the change from Baseline during the last two weeks of the Maintenance Treatment will be the basis for comparison between the two treatment groups.

Panic attack frequency over two-week intervals will be plotted. Similarly, the mean (\pm SD) absolute values and changes from baseline will be plotted by study analysis period and treatment group.

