### **9.3.3.2. Change From Baseline in Panic Attack Frequency During the Last 2 Weeks of the Maintenance Treatment Period**

The second key secondary estimand has the following attributes:

1. Treatments as randomized

2. The population defined by the inclusion/exclusion criteria of the trial as the primary population of interest
3. The change from baseline in panic attack frequency during the last 2 weeks of the Maintenance Treatment Period as the endpoint of interest
4. The population level summary of interest is the estimated treatment differences in median and the 95% Hodges-Lehmann CI
5. A composite strategy will be used to handle missing values due to ICEs. The cases of potential treatment-related ICEs described in [Section 9.3.3.1](#) will be assigned the worst rank and other cases of missing outcomes from ICEs will be assigned the second worst rank. The individual cases of treatment-related ICEs will be pre-identified prior to database lock.

The change from Baseline to each trial visit in frequency of panic attacks will be summarized by visit and treatment group. A non-parametric analysis using Mann-Whitney test performed on the change from Baseline during the last 2 weeks of the Maintenance Treatment Period will be the basis for comparison between the 2 treatment groups. A supportive analysis of frequency of panic attacks recorded at each visit will be performed using a Poisson or negative binomial regression with fixed effect of treatment group, visits, evidence-based psychotherapy use, and interaction between treatment group and visit. The Baseline panic attack frequency will be included as a covariate. Subject will be included as a random effect.

Sensitivity analysis will include all participants regardless of panic attack eDiary version used.

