1.2. Sample Size Considerations

A sample size of 114 participants per group (total of 228 participants) will provide at least 80% power to detect a difference of approximately 20% in proportion of participants (e.g., 60% of darigabat group versus 40% of placebo group) free of panic attacks at Week 14 at $\alpha=0.05$ (2-sided).

Two-hundred forty-six participants will be randomized to account for 18 participants whose panic attack assessments were made prior to implementation of protocol eDiary requirements (i.e., assessments recorded contemporaneous to the day being assessed [minimizing any potential recall bias] and records of the presence as well as the absence of each DSM-5-TR panic attack symptom associated with a given panic attack [distinguishing between missing data and the absence of a specific symptom]).

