5.5. Strata and Covariates

The randomization will be stratified by evidence-based psychotherapy for the treatment of anxiety disorders including panic disorder with 2 strata: receiving evidence-based psychotherapy (initiated >3 months prior to the Screening Visit) or not receiving evidence-based psychotherapy. The baseline value of each efficacy variable will be included as a covariate in the efficacy analyses based off collection in CRF. For analysis of freedom from panic attacks and panic attack frequency, baseline PDSS score will also be included as a covariate.

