5.11.2. Main Analytical Approach

The number and proportion of participants who are free of panic attacks during the last two weeks of the Maintenance Treatment will be summarized by analysis period and treatment group. The binomial repeated measures will be analyzed using the SAS[®] GENMOD procedure with logit link. The Baseline PDSS total score will be included as a covariate, and the treatment group, analysis periods, evidence-based psychotherapy use, and interaction between treatment group and analysis period will be included as fixed effects. Model diagnostics will be performed to explore the goodness-of-fit. An unstructured covariance matrix will be used for the repeated measures model. If the sparseness of the data results in model convergence or other issues, affecting reliability of estimates, efficacy conclusions will be based on the sensitivity analysis using the Fisher's exact test described in [Section 5.11.3](#). The odds ratio of active dose to placebo at the endpoint analysis period will be estimated based on the least squares mean difference in logit between the treatment groups from the GENMOD model with the associated 95% CI and p-values.

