5.14. Other Secondary Efficacy and Exploratory Analyses

All other secondary efficacy endpoints will be summarized using descriptive statistics by treatment group and visit, if appropriate. Statistical comparisons for each endpoint will be constructed without adjustment for multiple endpoints.

The other secondary efficacy endpoints are:

- Analysis at all time points in the proportion of participants free of panic attacks as assessed by participant daily diary. The baseline PDSS score will be used as the covariate.
- Change from baseline at all time points in the PDSS total score and subscores. The baseline PDSS total score will be used as the covariate.
- Change from baseline at all time points in panic attack frequency. The baseline panic attack frequency will be used as the covariate.
- Change from baseline in the CGI-S score at all time points. The baseline CGI-S score will be used as the covariate and derived as the score obtained
- Change from baseline in the HAM-A total scores. The baseline HAM-A total score will be used as the covariate.
- Change from baseline in the EQ-5D-5L at all time points. The baseline EQ-5D-5L index score will be used as the covariate.
- Change from baseline in the SDS total score at all time points. The baseline SDS total score will be used as the covariate.

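### The SAP promises baseline covariates for panic attack frequency, but the only method it gives is a Mann-Whitney test on change, which cannot use them; no adjusted frequency analysis remains

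*SAP*

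**What the plan says.** SAP 5.5 sets a general rule that the baseline value of each efficacy variable enters the efficacy analyses as a covariate. It then adds: "For analysis of freedom from panic attacks and panic attack frequency, baseline PDSS score will also be included as a covariate".

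SAP 5.14, on change in frequency at all time points, states: "The baseline panic attack frequency will be used as the covariate".

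SAP 5.15 assigns that same endpoint to the methods of 5.12.2.2. There the basis for comparing the groups is "A non-parametric analysis using Mann-Whitney test performed on the change from Baseline during the last two weeks of the Maintenance Treatment", reported with a Hodges-Lehmann median difference and 95% interval. The summary table in 5.13 repeats this. The only sensitivity analysis (5.12.2.3) adds participants who used the other eDiary version.

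Protocol 9.3.3.2 has the same Mann-Whitney test as its main comparison. It also plans a supportive Poisson or negative binomial regression with psychotherapy use as a fixed effect, and says: "The Baseline panic attack frequency will be included as a covariate". That model does not appear in the SAP. SAP section 6 says only that most sensitivity analyses were removed.

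**The concern.** The covariate rule and the method cannot both be carried out. A programmer who follows 5.12.2.2 breaks 5.5 and 5.14. One who follows 5.5 and 5.14 has to invent a method. If the gap is settled after unblinding, the choice can be influenced by the result.

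There is also a cost in precision. A change score fixes the coefficient on baseline at 1, while analysis of covariance estimates it. Unless follow-up frequency rises one for one with baseline frequency, the change score carries avoidable noise. SAP section 6 already accepts that the trial, closed early, has too little power for hypothesis tests. The width of the intervals is then much of what the efficacy analysis can offer.

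**Working it through.** **The plan's own figure.** The documents give no power or precision figure for frequency. The only one is for the primary endpoint in SAP 1.2: "A sample size of 114 participants per group (total of 228 participants) will provide at least 80% power" for "60% of darigabat group versus 40% of placebo group", two-sided 5%. By the normal approximation, power = Φ[(0.2√114 − 1.96√(2 × 0.5 × 0.5)) / √(0.24 + 0.24)] = Φ[(2.135 − 1.386)/0.693] = Φ(1.08) = 86.0%. The exact Fisher test gives 83.8%. The stated figure holds, but it says nothing about frequency.

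**Can the sections be reconciled as written?**

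| SAP section | Covariates promised or usable for frequency |
|---|---|
| 5.5 | baseline frequency (general rule) and baseline PDSS |
| 5.14 (all time points) | baseline frequency |
| 5.15 (all time points) | whatever 5.12.2.2 provides |
| 5.12.2.2 | none; baseline enters only by subtraction |

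They cannot. For the key secondary comparison, 5.5 conflicts with 5.12.2.2. For all time points, 5.14 conflicts with 5.15.

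**Size of the precision loss.** The inputs are r, the baseline to follow-up correlation, and k, the ratio of follow-up SD to baseline SD. Neither is in the documents, so both are assumed. In units of the baseline variance:

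- Var(change) = 1 + k² − 2rk
- Var(ANCOVA) = k²(1 − r²)

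With k = 1 the ratio is (1 − r²)/[2(1 − r)] = (1 + r)/2.

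| r (assumed) | Var(ANCOVA) / Var(change) | Interval width ratio (square root) | Narrower by |
|---|---|---|---|
| 0.3 | 0.91/1.40 = 0.65 | 0.806 | about 19% |
| 0.5 | 0.75/1.00 = 0.75 | 0.866 | about 13% |
| 0.7 | 0.51/0.60 = 0.85 | 0.922 | about 8% |

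If the spread shrinks as counts fall, the gap grows. At r = 0.5 and k = 0.7 the ratio is (0.49 × 0.75)/(1 + 0.49 − 0.70) = 0.3675/0.79 = 0.47. The loss vanishes when rk = 1. These are normal-theory guides to a rank test.

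**Simulation on assumed counts.** There were 114 per group, 1,000 replicates per scenario and complete data for one period. Baseline counts were overdispersed and restricted to at least 4 attacks. The treatment rate ratio was 0.5 to 0.75, and 20% were in psychotherapy. Power:

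| Spearman correlation | Mann-Whitney on change | Rank ANCOVA on baseline frequency | Gain (points) |
|---|---|---|---|
| 0.17 | 27.5% | 63.3% | 35.8 |
| 0.21 | 47.3% | 80.7% | 33.4 |
| 0.29 | 39.7% | 66.1% | 26.4 |
| 0.42 | 32.6% | 61.7% | 29.1 |
| 0.57 | 35.0% | 74.4% | 39.4 |

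The gains depend on the assumed dispersion and fall in counts, and 114 per group will not be reached. I use them for direction only. In the same scenarios:

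- Adding only the stratum to the rank analysis changed power by less than 1 point.
- Adding log baseline frequency to a stratum-adjusted logistic model for panic-free status changed power by −1 to +2 points.
- Fisher's test was 3.5 to 6 points below the stratum-adjusted logistic model.

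**The case against.** The strongest reply is that Mann-Whitney on change was already the protocol's main comparison, that it does use baseline by subtraction, and that the SAP openly reduces its scope to an exploratory evaluation. Dropping a supportive model fits that reduction. The declared population summary in SAP 5.12.2.1 is a median difference with a Hodges-Lehmann interval, which goes with Mann-Whitney and not with a rank analysis of covariance.

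Much of this stands. It is wrong to say that the test ignores baseline frequency, and replacing Mann-Whitney outright would separate the test from its declared estimate. Exploratory status also takes weight off lost power as such. But none of it reconciles 5.5 and 5.14 with 5.12.2.2 and 5.15, and an exploratory analysis still benefits from tighter estimates.

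A reader might infer three stronger points that the documents do not support:

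- **That the primary model is defective because it omits baseline frequency.** SAP 5.11.2 includes psychotherapy use, and "The Baseline PDSS total score will be included as a covariate"; 5.14 names the same covariate for that endpoint. The baseline value of panic-free status is constant, because eligibility requires at least 4 attacks. The simulated gain from adding frequency is negligible, and 5.11.2 already anticipates convergence trouble from sparse data.
- **That leaving out the stratum costs material power.** Randomisation is stratified on it, which limits imbalance, and the simulated effect is under 1 point.
- **That Fisher's test must be replaced.** It is an unadjusted sensitivity analysis by design, and it carries the conclusion only if the model proves unreliable. SAP 5.11.3 also asks for an exact interval on the group difference, which a Cochran-Mantel-Haenszel test would not supply.

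**Conclusion.** The point holds for panic attack frequency only. The contradiction between SAP 5.5 and 5.14 on one side and 5.12.2.2 and 5.15 on the other can be read directly from the text and needs no assumption. So can the absence of any covariate-adjusted frequency analysis from the SAP.

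The size does rest on assumptions. With equal variances and normal theory, an adjusted analysis has 65% to 85% of the change-score variance for r from 0.3 to 0.7, which means intervals about 19% to 8% narrower. The simulated gains point the same way but depend on assumed dispersion, correlation and complete data. The consequence is for the consistency of the plan and the precision of an exploratory result. No confirmatory claim is at risk.

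**What to change.** Before unblinding, prespecify one covariate-adjusted frequency analysis in SAP 5.12.2 and make 5.5, 5.14 and 5.15 refer to it. Either of these would do:

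- a rank analysis of covariance of the change on baseline frequency, stratified by psychotherapy; or
- a negative binomial model of the attack count, with log completed diary days as offset and baseline frequency, baseline PDSS and stratum as covariates. The offset matches 3.1.1.1, which already divides attacks by completed diary days. This goes beyond the protocol's supportive model, which had neither offset nor PDSS.

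If the rank option is chosen, 5.5 should say how baseline PDSS is handled for this endpoint. Keep the Hodges-Lehmann median difference and interval as the effect estimate. As an option, report an exact Cochran-Mantel-Haenszel test stratified by psychotherapy beside Fisher's test, for the case where the fallback in 5.11.2 is used.

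The cost is SAP wording and a few lines of code; all the variables are already collected. The drawback is that the adjusted test does not map exactly to the Hodges-Lehmann estimate. The Hodges-Lehmann interval itself will not narrow, because the gain appears in the adjusted analysis reported beside it.

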5.12.2.3. Sensitivity Analyses

Sensitivity analysis will include all participants regardless of panic attack eDiary version used.

5.13. Summary of Primary and Key Secondary Efficacy Analyses

ICE Strategy	Primary Analysis	Sensitivity Analysis
Primary Endpoint: Proportion of participants who are free of panic attacks during the last two weeks of the Maintenance Treatment Period		
Hypothetical strategy with data prior to treatment discontinuation used in a repeated measures analysis last two weeks	
 • The population defined by the inclusion/exclusion criteria of the trial • Treatment as randomized • Binomial repeated measures described in Section 5.11.2 	
 • Fisher's exact test • Include all participants regardless of panic attack eDiary version used • Analysis using modified definition of outcome requiring complete eDiary compliance
Key Secondary Endpoint: Change from baseline in PDSS total score at Week 14 as the endpoint of interest		
Hypothetical strategy with data prior to treatment discontinuation used in a repeated measures analysis	
 • The population defined by the inclusion/exclusion criteria of the trial • Treatment as randomized • MMRM described in Section 5.12.1.2 	
 • None
Second Key Secondary Endpoint: Change from Baseline in panic attack frequency during the last two weeks of the Maintenance Treatment Period		
While-on-treatment strategy with data prior to treatment discontinuation used in the analysis	
 • The population defined by the inclusion/exclusion criteria of the trial as the primary population of interest • Treatment as randomized • Non-parametric analysis using Mann-Whitney test, median difference and 95% CI using Hodges-Lehmann estimation described in Section 5.12.2.2 	
 • Include all participants regardless of panic attack eDiary version used.

5.14. Other Secondary Efficacy and Exploratory Analyses

All other secondary efficacy endpoints will be summarized using descriptive statistics by treatment group and visit, if appropriate. Statistical comparisons for each endpoint will be constructed without adjustment for multiple endpoints.

The other secondary efficacy endpoints are:

- Analysis at all time points in the proportion of participants free of panic attacks as assessed by participant daily diary. The baseline PDSS score will be used as the covariate.
- Change from baseline at all time points in the PDSS total score and subscores. The baseline PDSS total score will be used as the covariate.
- Change from baseline at all time points in panic attack frequency. The baseline panic attack frequency will be used as the covariate.
- Change from baseline in the CGI-S score at all time points. The baseline CGI-S score will be used as the covariate and derived as the score obtained
- Change from baseline in the HAM-A total scores. The baseline HAM-A total score will be used as the covariate.
- Change from baseline in the EQ-5D-5L at all time points. The baseline EQ-5D-5L index score will be used as the covariate.
- Change from baseline in the SDS total score at all time points. The baseline SDS total score will be used as the covariate.

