5.12.1.2. Analytic Method

The change from Baseline to each trial visit in PDSS total score will be summarized by visit and treatment group. An MMRM analysis will be used with fixed effects of treatment group, visits, evidence-based psychotherapy use, and interaction between treatment group and visit. The baseline value of PDSS total score will be included as a covariate. Participant will be included as a random effect. An unstructured covariance structure will be used for the repeated measures. The Kenward-Roger approximation will be used to estimate the denominator degrees of freedom. If the unstructured covariance matrix results in convergence issue, the Fisher scoring algorithm may be used to obtain the initial values of covariance parameters. If convergence issues still cannot be resolved, a structured covariance matrix may be used with the heterogeneous Toeplitz covariance structure followed by the heterogeneous first-order autoregressive (AR[1]) structure. In the case that a structured covariance matrix needs to be used, a robust sandwich variance estimator will be used to address the potential adverse impact of covariance matrix misspecification. The difference between active dose and placebo at the endpoint visit will be estimated based on the least squares mean difference between the treatment groups at the endpoint visit from the MMRM with the associated 95% CI and p-values. The LS Mean (\pm SE) from the model will be plotted for change in PDSS total score during each visit by treatment group. Similarly, the mean (\pm SD) of absolute values and change from Baseline PDSS total score will be presented by visit and treatment group.

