5.15. Summary of Analyses of Other Efficacy and Exploratory Endpoints

Endpoint	Analysis Method
Analysis at all time points in the proportion of participants free of panic attacks as assessed by participant daily diary	Repeated measure logistic regression described in Section 5.11.2
Change from baseline at all time points in the PDSS total score and subscores	MMRM model described in Section 5.12.1.2
Change from baseline at all time points in panic attack frequency	Same methods described in Section 5.12.2.2
Change from baseline in the CGI-S score at all time points	MMRM model described in Section 5.12.1.2
Change from baseline in the HAM-A total score at all time points	MMRM model described in Section 5.12.1.2
Change from baseline in the EQ 5D-5L at all time points	MMRM model described in Section 5.12.1.2
Change from baseline in the SDS total score at all time points	MMRM model described in Section 5.12.1.2

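### SAP 5.14 adjusts PDSS subscores for the baseline total, at odds with (or at best unclear beside) the own-baseline rule in 5.5; usually a modest loss of precision

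*SAP*

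**What the plan says.** SAP 5.5 sets a general rule: "The baseline value of each efficacy variable will be included as a covariate in the efficacy analyses based off collection in CRF". Its one special case concerns the panic-attack endpoints: "For analysis of freedom from panic attacks and panic attack frequency, baseline PDSS score will also be included as a covariate". PDSS subscores are not mentioned there.

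SAP 5.14 handles the total and the subscores together in one bullet, and for both it says: "The baseline PDSS total score will be used as the covariate". SAP 5.15 assigns the same pair to the "MMRM model described in Section 5.12.1.2", and that section says: "The baseline value of PDSS total score will be included as a covariate".

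The other scales in the 5.14 list each get their own baseline. For HAM-A the text is "The baseline HAM-A total score will be used as the covariate"; CGI-S, SDS total and the EQ-5D-5L index follow the same pattern.

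The subscores are a listed secondary efficacy endpoint (SAP Section 2, Table 2), and 5.14 plans statistical comparisons for them. Neither 5.14 nor the list of changes in SAP Section 6 gives a reason for treating them differently from the other scales.

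**The concern.** Change in a subscore is usually tied most closely to that subscore's own starting value, through regression to the mean. The baseline total contains the subscore but mixes it with other items, so it captures that relation only in part. What it misses stays in the residual variance and widens the confidence interval for the treatment difference. A chance difference between arms in the baseline subscore is also only partly corrected.

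SAP Section 6 concedes that early closure leaves too little power for hypothesis tests. Precision is then most of what these analyses can offer, and the items needed for the better covariate are already collected at baseline. There is a practical side too: two programmers reading 5.5 and 5.14 could fit different models and each claim to follow the plan.

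**Working it through.** The plan gives no figure for the subscore analyses, so there is nothing to reproduce. The check compares residual variances at one follow-up visit. It ignores the other model terms, which are the same under either choice.

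**Setup.** X is the baseline subscore, scaled to SD 1; T the baseline total; Y the follow-up subscore. Let r = corr(X, Y), t = corr(X, T) and s = SD(Y)/SD(X). Assume T predicts Y only through X.

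- Adjusting Y − X for X leaves variance s²(1 − r²).
- Adjusting Y − X for T leaves s²(1 − r²) + (1 − rs)²(1 − t²).
- Ratio, total-adjusted to own-adjusted: 1 + (1 − rs)²(1 − t²) / [s²(1 − r²)].

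The ratio is never below 1 under this assumption. It equals 1 when t = 1 or rs = 1.

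**Value of t.** The documents give no correlations. The PDSS has seven items, described as five core-symptom items and two impairment items (Protocol 8.1.2, SAP 3.1.2). If items have equal variances and a common correlation p, a k-item subscore has t² = k(1 + 6p) / [7(1 + (k − 1)p)]. With p = 0.3 assumed:

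- k = 5: t² = 14/15.4 = 0.909, t = 0.95
- k = 2: t² = 5.6/9.1 = 0.615, t = 0.78
- k = 1: t² = 2.8/7 = 0.400, t = 0.63

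**Central case, r = 0.5 and s = 1 (both assumed).** The ratio is 1 + 0.25(1 − t²)/0.75 = 1 + (1 − t²)/3.

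| Subscore | Variance ratio | SE increase | Effective sample lost (1 − 1/ratio) |
|---|---|---|---|
| 5 items | 1 + 0.091/3 = 1.030 | 1.5% | 2.9% |
| 2 items | 1 + 0.385/3 = 1.128 | 6.2% | 11.4% |
| 1 item | 1 + 0.600/3 = 1.200 | 9.5% | 16.7% |

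**Sensitivity of the SE increase (same t).** The multiplier of (1 − t²) is (1 − rs)²/[s²(1 − r²)].

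| r, s | Multiplier | 5 items | 2 items | 1 item |
|---|---|---|---|---|
| 0.3, 1 | 0.49/0.91 = 0.538 | 2.4% | 9.9% | 15.0% |
| 0.7, 1 | 0.09/0.51 = 0.176 | 0.8% | 3.3% | 5.2% |
| 0.5, 1.25 | 0.1406/1.1719 = 0.120 | 0.5% | 2.3% | 3.5% |
| 0.5, 1.5 | 0.0625/1.6875 = 0.037 | 0.2% | 0.7% | 1.1% |

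A value of s above 1 is plausible because entry requires a PDSS total of at least 12 at both Screening and Baseline (Protocol 5.1, criterion 4), which narrows the baseline spread.

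**If T carries information beyond X.** Take s = 1, r = 0.5, t = 0.8. With a partial correlation of T and Y given X of +0.2, the ratio is 1.216; with −0.2 it is 0.995. In both cases, using X and T together gives 0.960 of the variance from X alone. So the total can match or slightly beat the own baseline, but only when the other items predict the follow-up subscore negatively. Including both covariates does no worse, apart from one degree of freedom.

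**The case against.** The strongest reply is that the SAP may already require the own baseline. Section 5.5 says it is included, and 5.14 does not exclude it. The covariate lines in 5.14 are evidently not exhaustive: for panic attack frequency, 5.5 adds baseline PDSS, yet 5.14 names only baseline frequency. Nor can the pointer from 5.15 to 5.12.1.2 be literal, since CGI-S, HAM-A, EQ-5D-5L and SDS are sent to the same model and yet 5.14 gives each its own baseline. On an additive reading there is no loss.

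This stands as far as it goes: the text cannot be called a certain contradiction. But 5.14 speaks of a single covariate, and where 5.5 means to add a term it says so. The additive reading shows that the plan supports two models, which is itself a reason to settle the wording.

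The second reply concerns size, and it also stands. A reader who assumed subscore-to-total correlations of 0.5 to 0.7, with r from 0.3 to 0.5 and equal standard deviations, would infer standard errors 8% to 18% too large for subscores generally. The documents do not support that. The total contains the subscore, and the proration rule in SAP 3.1.2.1 implies multi-item subscales. For five of seven items, t is 0.85 (√(5/7)) even with uncorrelated items, which at r = 0.5 and s = 1 gives a variance ratio of 1 + (2/7)/3 = 1.095 and an SE increase of 4.7%. Correlations of 0.5 to 0.7 suit single items or a short subscore.

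**Conclusion.** The point holds as a drafting conflict or ambiguity with a usually modest cost in precision. Under the central assumptions (r = 0.5, equal standard deviations, inter-item correlation 0.3), following 5.14 literally raises the standard error by about 1.5%, 6% and 10% for five-item, two-item and single-item subscores. The loss vanishes as rs approaches 1. All of these inputs are assumed, so the figures are illustrations of a range.

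Three further inferences are tempting but unsupported. The covariate choice does not bias the treatment contrast, because randomisation protects it under either model. Baseline imbalance in the subscore is not left wholly uncorrected, because the total includes the subscore. The key secondary PDSS analysis is not affected, because the total is its own baseline.

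Priority is minor. The subscores are non-key, no decision rule rests on them, and SAP Section 6 declares the efficacy analysis exploratory.

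**What to change.** In SAP 5.14, keep the baseline total as covariate for the PDSS total score, and state that each subscore is adjusted for its own baseline subscore, optionally with the baseline total as well. Carry the same wording into 5.15, because its pointer to 5.12.1.2 otherwise brings the total back in. Name the items that make up each subscore; neither document does so explicitly, and the covariate cannot be programmed without it.

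The cost is a few lines of text and no new data. Using both covariates costs one degree of freedom. SAP Section 7 records a single finalised version, so if that version stands, the choice can be documented in the study report, as Section 6 provides for deviations, and preferably fixed before unblinding.
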